#### **4.5.2.2. Deaths**

All deaths will be summarized based on the number and percentage of participants. This summary will classify participants by time of death relative to the last dose of medication ( $>30$  days or  $\leq 30$  days) and analyze the primary cause of death in the order listed in the CRF. A supportive listing will be generated to provide participant-specific details on participants who died.

#### **4.5.2.3. Adverse Events Leading to Discontinuation of Study Treatment and Other Significant Adverse Events**

The following categories of AEs will be summarized separately in descending order of total incidence by PT only and separate supportive listings will be generated with participant level details for those participants:

- AEs leading to permanent discontinuation of study treatment
- AEs leading to dose delays
- AEs leading to dose interruptions
- AEs leading to dose reductions

Only listings will be provided for the following:

- AEs leading to infusion stopped early and not completed
- AEs leading to infusion interrupted but completed

#### 4.5.2.4. COVID-19 Assessment and COVID-19 AEs

A standardized MedDRA Query (SMQ) will be used to identify all COVID-19 AEs.

The overall incidence of AEs and SAEs of COVID-19, COVID-19 AEs leading to study intervention discontinuation, COVID-19 AEs leading to study withdrawal, and Grade 3 and 4 COVID-19 AEs will be summarized. The incidence of these events at individual PT level can be obtained from the standard AE/SAE summaries.

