#### **4.5.2. Adverse Events**

Adverse events analyses including the analysis of adverse events (AEs), Serious AEs (SAEs) and other significant AEs will be based on GSK Core Data Standards.

An overview summary of AEs, including counts and percentages of participants with any AE, AEs related to study intervention, Grade 3 and 4 AEs, Grade 3 and 4 AEs related to study intervention, AEs leading to permanent discontinuation of study intervention, study intervention related AEs leading to permanent discontinuation of study intervention, AE leading to dose reductions, AEs leading to dose delays, SAEs, SAEs related to study intervention, fatal SAEs, and fatal SAEs related to study intervention will be produced. Unless otherwise specified, AEs will be summarized by treatment arms. AEs related to pomalidomide and dexamethasone separately, OR pomalidomide and dexamethasone in combo will all be considered as AEs related to the pom/dex regimen and summarized under the pom/dex treatment arm. Adverse events will be coded using the standard Medical Dictionary for Regulatory Affairs (MedDRA dictionary) and graded by the investigator according to the NCI-CTCAE, (version 5.0).

A summary of number and percentage of participants with any adverse events by maximum grade will be produced. AEs will be sorted by Preferred term (PT) in descending order. The summary will use the following algorithms for counting the participant:

- **Preferred term row:** Participants experiencing the same AE preferred term several times with different grades will only be counted once with the maximum grade.
- **Any event row:** Each participant with at least one adverse event will be counted only once at the maximum grade no matter how many events they have.

The frequency and percentage of AEs (all grades) will be summarized and displayed in two ways: 1) in descending order by PT only and 2) in descending order by SOC and PT. In the SOC row, the number of participants with multiple events under the same SOC will be counted once.

A summary of number and percentage of participants with treatment-emergent AEs by maximum grade will be also produced.

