A separate summary will be provided for study intervention-related AEs. A study intervention-related AE is defined as an AE for which the investigator classifies the possible relationship to study intervention as “Yes”. A worst-case scenario approach will be taken to handle missing relatedness data, i.e. the summary table will include events with the relationship to study intervention as ‘Yes’ or missing. The summary table will be displayed in two ways: 1) by maximum grade sorted by PT in descending order and 2) in descending order by SOC and PT.

A summary of cumulative incidence of AE by number of cycles (<=1, <=2, <=4, <=6, <=8, <=10, Any) received at first occurrence will be provided.

In addition, AEs of maximum grade of 3 or higher will be summarized separately by PT.

All SAEs will be tabulated based on the number and percentage of participants who experienced the event. Separate summaries will also be provided for study intervention-related SAEs. The summary tables will be displayed by PT. The summary of all SAEs will also be created by SOC and PT. In addition, a summary of cumulative incidence of SAE by number of cycles (<=1, <=2, <=4, <=6, <=8, <=10, Any) received at first occurrence will be provided.

A study intervention-related SAE is defined as an SAE for which the investigator classifies the relationship to study intervention as “Yes”. A worst-case scenario approach will be taken to handle missing data, i.e. the summary table will include events with the relationship to study intervention as ‘Yes’ or missing.

A summary of non-serious AEs that occurred in 5% of the participants or above will be provided (no rounding for the percentage will be used in terms of 5% threshold, e.g., event with 4.9% incidence rate should not be included in this table). The summary will be displayed by SOC and PT.

All AEs will be listed. Additionally, a listing of subject IDs for each individual AE will be produced. Separate supportive listings with participant-level details will be generated for fatal and non-fatal SAEs, respectively. The relationship between MedDRA SOC, PT, and Verbatim Text will be listed.

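### The only severity row in the COVID-19 AE summary stops at Grade 4 and has no fatal row beside it, so fatal cases are left out of the severe COVID-19 count

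*SAP*

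**What the plan says.** Section 4.5.2.4 identifies COVID-19 AEs by a standardized MedDRA query (SMQ) and then names five items to summarize. The first three are given as "The overall incidence of AEs and SAEs of COVID-19, COVID-19 AEs leading to study intervention discontinuation". The remaining two are given as "COVID-19 AEs leading to study withdrawal, and Grade 3 and 4 COVID-19 AEs will be summarized". For detail by preferred term (PT), the section relies on other tables: "The incidence of these events at individual PT level can be obtained from the standard AE/SAE summaries".

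The general rules are in section 4.5.2. AEs are "graded by the investigator according to the NCI-CTCAE, (version 5.0"). The AE overview there also has a Grade 3 and 4 row, but its list of rows ends with "SAEs, SAEs related to study intervention, fatal SAEs, and fatal SAEs related to study intervention will be produced". A further table states that "AEs of maximum grade of 3 or higher will be summarized separately by PT". For the any-event row of the maximum-grade table the counting rule is: "Each participant with at least one adverse event will be counted only once at the maximum grade no matter how many events they have". Section 4.5.2.4 states no counting rule of its own.

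**The concern.** The CTCAE scale that the SAP adopts assigns Grade 5 to death. A row restricted to Grades 3 and 4 therefore leaves out the worst outcome, and the COVID-19 summary has no fatal row to bring it back. COVID-19 can be fatal, so this is a realistic case.

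What is at stake is how one descriptive safety row reads. When a severe case becomes fatal, the participant can move out of the row. Between two arms with the same proportion of severe-or-fatal cases, the arm with more deaths would then show the lower figure on the only severity measure taken over the whole SMQ.

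**Working it through.** No figure in the plan needs reproducing and no rate is given, so the check compares the planned displays and follows one participant through them.

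**Step 1. The three grade-based rules side by side**

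- COVID-19 summary (4.5.2.4): Grade 3 and 4; no fatal row.
- General AE overview (4.5.2): Grade 3 and 4; fatal SAE rows added.
- Severe AEs by PT (4.5.2): all grades from 3 upward, so fatal events are included.

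Each of the two general displays has a way of catching deaths. The COVID-19 summary has none.

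**Step 2. One participant with a single, treatment-emergent, fatal COVID-19 event (Grade 5)**

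- COVID-19 AE row: counted, 1.
- COVID-19 SAE row: counted, 1, because a fatal event is serious.
- Grade 3 and 4 row: not counted, 0.

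**Step 3. Size of the shortfall**

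Within an arm, let *a* be the number of participants with maximum COVID-19 grade 3 or 4, and *f* the number with maximum grade 5.

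- Row as worded, one count at maximum grade: *a*.
- Row worded as Grade 3 or higher: *a* + *f*.
- Shortfall: (*a* + *f*) − *a* = *f*.

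If the row instead counts anyone with any Grade 3 or 4 COVID-19 record, let *k* of the *f* participants have such a record separate from the fatal one. The row then shows *a* + *k*, and the shortfall is *f* − *k*, somewhere between 0 and *f*. Section 4.5.2.4 does not say which rule applies.

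**Step 4. Can *f* or *a* + *f* be recovered from other planned displays?**

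- *SAE row minus Grade 3 and 4 row:* no. Seriousness and grade are different classifications, and the SAE row mixes fatal with non-fatal cases.
- *Tables by PT (4.5.2):* not reliably. One participant may have several terms in the SMQ, so PT counts do not add up to participants.
- *Fatal SAE rows of the general overview (4.5.2):* no. They cover all causes together.
- *Death summary (4.5.2.2):* only if the CRF has COVID-19 as a cause category, which the SAP does not say.
- *COVID-19 infection summaries (6.1.6):* no. They cover case status and test results, not grade or outcome.
- *Listings of fatal SAEs and of deaths:* yes for fatal cases, but by hand count.

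No planned table is therefore sure to give, by arm, the number of participants with a severe-or-fatal COVID-19 event over the SMQ.

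**The case against.** The strongest reply is that little is lost. A treatment-emergent fatal COVID-19 event leaves at most one of five rows. It stays in the COVID-19 AE and SAE rows, the tables by PT and maximum grade, the table of AEs from Grade 3 upward, the fatal SAE listing and the death summary. Section 1 also leaves display detail to a separate programming specification, which may settle the counting rule. All of this stands, and it limits the point to one row.

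It does not remove the point. The restriction to Grades 3 and 4 is written in the SAP itself, and the other displays do not supply the missing participant-level count.

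A reader might infer more than the document supports:

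- *That the COVID-19 summary counts only Grade 3 and 4 events, or that COVID-19 deaths vanish from the report.* Neither is so, as the displays just listed show.
- *That the gap impairs interpretation of PFS and OS.* All AE displays are limited by section 6.2.3 to the treatment-emergent window: up to 70 days after treatment stop, or the start of new anti-cancer therapy if earlier. A fatal COVID-19 row would miss later deaths that count for OS. The summary of all deaths by cause is closer to that need and is already planned.
- *That a large share of severe cases, perhaps half, would be missing.* That follows only if fatal and non-fatal severe cases are assumed equally common. The SAP gives no rate for either.
- *That section 4.5.2.5 removes other COVID-19 reporting.* It declines to assess the pandemic's impact on safety results, with before-and-after tables as its example. Infections (6.1.6), reasons for withdrawal and discontinuation (6.1.1) and important deviations (6.1.3) are still reported with respect to COVID-19.

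**Conclusion.** The point holds as a limited reporting inconsistency. The only grade-based COVID-19 row leaves out fatal cases, contrary to the practice of section 4.5.2, and no planned table is sure to give the by-arm count of severe-or-fatal COVID-19 cases.

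The shortfall equals the number of participants with maximum COVID-19 grade 5. This rests on two assumptions: fatal events are recorded as Grade 5 under CTCAE version 5.0, and each participant is counted once at maximum grade. If any Grade 3 or 4 record is enough to be counted, that number is an upper limit. The SAP does not give the number, and it could be zero.

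No estimand, hypothesis test or error rate is affected. The change is still worth making, because the row as worded can favour the arm with more COVID-19 deaths.

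**What to change.** In section 4.5.2.4:

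- Replace the Grade 3 and 4 item with *COVID-19 AEs of maximum Grade 3 or higher*.
- Add a row *fatal COVID-19 SAEs*.
- State that both rows are shown by treatment arm and count each participant once, over all terms in the COVID-19 SMQ.

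This brings the section into line with the overview and the severe-event table in section 4.5.2. The cost is one phrase, one table row and a sentence on counting. Grade, seriousness and outcome are already needed for the displays in section 4.5.2, so no new data are required.

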#### 4.5.2.5. Impact of COVID-19 Pandemic on Safety Results

The study began in most countries after the pandemic began. Hence, the impact of the COVID-19 pandemic on the safety results will not be assessed, e.g. tables showing incidence rates for events occurring before and after the start of the COVID-19 pandemic won't be produced.

### 4.5.3. Ocular Findings on Ophthalmic Exam

#### 4.5.3.1. Ocular Exam and Visual Acuity

As outlined in study protocol (GlaxoSmithKline Document Number: [2017N336101\\_00](#)) Schedule of Activities (Section 2 of the protocol), ocular exams are scheduled at screening, while on treatment, and at end of treatment for participants in both arms. Ocular exams in follow-up period (if needed) will only be conducted for Arm 1 (belantamab mafodotin). The ocular findings and visual acuity from ocular exams will be summarized descriptively:

- **From baseline to last follow-up, the following analyses will be performed**

- i. Visual acuity

- The best corrected visual acuity (BCVA) summary will be based on the Logarithm of the Minimum Angle of Resolution (logMAR score), where:
 
$$\text{logMAR score} = -\log_{10}(\text{Snellen Acuity Score})$$
- The following categories of logMAR score changes from baseline are defined: No change/improved vision is defined as a change from baseline  $<0.12$ ; a possible worsened vision is defined as a change from baseline  $\geq 0.12$  to  $<0.3$ ; a definite worsened vision is defined as a change from baseline  $\geq 0.3$  logMAR score.
- A summary of characteristics of worsened vision (logMAR Score change from baseline  $\geq 0.12$ ) by subject will be provided, including time to onset of first occurrence: summary statistics and frequency/percentage in categories (1-21, 22-42, 43-63, 64-105, >105 days); outcome of first occurrence, duration of first occurrence: summary statistics and frequency/percentage in categories (1-21, 22-42, 43-63, 64-105, >105 days); number of occurrences based on participants with worsened vision; outcome post treatment exposure; time to resolution post treatment exposure, outcome of last event. The duration is defined as time from onset of worsened vision to the first time the subject is free of worsened vision (i.e. free of  $\geq 0.12$  logMAR Score change from

baseline). It requires at least one day gap between the resolution of all worsened vision from first occurrence to the onset of second occurrence.

- In addition, a summary of worst change from baseline (based on the eye with worst change) in BCVA Score (logMAR Score) will be provided for categories “increase  $\geq 0.12$  to  $< 0.3$ ”, “increase  $\geq 0.3$  to  $< 0.6$ ”, “increase  $\geq 0.6$ ”.
- Shift table for visual acuity from baseline to worst case post-baseline by eye (R/L) will be provided

ii. Corneal Exam

- Shift table from baseline to worst case post-baseline by eye (R/L) for corneal epithelium findings:
  - Corneal epithelium (Normal to Abnormal),
  - Microcyst-like deposits (No to Yes).
  - Subepithelial haze (No to Yes)
  - Stromal opacity (No to Yes)
  - Epithelial edema (No to Yes)
  - Corneal epithelia defect (No to Yes)
  - Corneal erosion (No to Yes)
  - Corneal ulcer (No to Yes)
  - Corneal neovascularization (No to Yes)
  - Superficial punctate keratopathy severity (No to yes)
  - Stippled peripheral corneal staining  $\pm$  vortex/whorl staining pattern (No to Yes), summarize only for patients enrolled under protocol amendment 1.

iii. Lens

- Shift table from baseline to worst case post-baseline by eye (R/L) for lens findings:
  - Cataract (No to Yes)

Supportive listings may be provided, e.g.

- Listing of participants which fall into each of the two categories of change from baseline in BCVA: “possible worsened vision”, “definite worsened vision” with sub-categories “increase  $\geq 0.3$  to  $< 0.6$ ”, and “increase  $\geq 0.6$ ”.
- Listing of participants who fall into each of the two categories of decline in BCVA to ‘light perception’ (LP) or ‘no light perception’ (NLP) anytime post-baseline.
- Listings of participants with cataracts at baseline, pseudophakia at Baseline, who developed cataracts post-baseline, and who underwent cataract surgery post-baseline will be provided.
- Listing of impact on driving and reading if data are available
- Listing of corneal exam results

Details of the displays are to be provided in Output and Programming Specification document.

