**6.2.5. Assessment Window**

For data summaries by visit, scheduled visits with nominal visit description as well as the worst-case post baseline will be displayed. Unscheduled visits will not be displayed or slotted into a visit window but will be included in the derivation of worst-case post baseline assessment. All un-scheduled visits will be displayed in the listing.

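### The worst-case ocular tables in SAP Section 4.5.3.1 run to last follow-up, a period in which only Arm 1 has eye exams; a version over a window scheduled in both arms should be added.

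*SAP*

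**What the plan says.** SAP Section 4.5.3.1 describes the exam schedule in two sentences. First, "ocular exams are scheduled at screening, while on treatment, and at end of treatment for participants in both arms". Second, "Ocular exams in follow-up period (if needed) will only be conducted for Arm 1 (belantamab mafodotin", that is, the experimental arm alone.

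It then opens one bullet that governs everything below it: "From baseline to last follow-up, the following analyses will be performed". Under that bullet stand:

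- for visual acuity, "a summary of worst change from baseline (based on the eye with worst change) in BCVA Score (logMAR Score) will be provided", and also "Shift table for visual acuity from baseline to worst case post-baseline by eye (R/L) will be provided";
- for the cornea, "Shift table from baseline to worst case post-baseline by eye (R/L) for corneal epithelium findings";
- for the lens, "Shift table from baseline to worst case post-baseline by eye (R/L) for lens findings";
- a table of the characteristics of worsened vision, which includes outcome and time to resolution after treatment exposure.

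Section 6.2.5 adds that unscheduled visits "will be included in the derivation of worst-case post baseline assessment", with no time limit. Section 4.5.3.2 defines an end of treatment exposure for each arm, but for its characteristics tables, not as a cut-off for the worst-case tables of Section 4.5.3.1. Section 1.1.1 lists ocular findings as an endpoint of the objective that sets the safety of belantamab mafodotin against that of pom/dex.

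**The concern.** A worst-case value is a maximum over all exams in the window. It can only stay the same or get worse as exams are added. If one arm has exams in a period when the other has none, the two columns of a worst-case table are not built from the same observation, and part of any difference may come from the extra looking.

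The same gap affects the post-exposure items in the opposite sense. Whether and when a finding resolves after treatment can be seen only if someone examines the eye after treatment. In Arm 2 there is little to report after the end-of-treatment exam, so an entry for that arm would mostly reflect absence of data.

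The stake is how a secondary safety endpoint is read. Corneal events are also an adverse event of special interest (Section 4.5.2.1), so these tables will be looked at closely.

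**Working it through.** The SAP gives no figure on this point, so there is none to reproduce. The check is of the text, followed by an illustration on stated assumptions.

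**1. Exam schedule against analysis window (Section 4.5.3.1)**

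| Period | Arm 1 exams | Arm 2 exams | Inside the analysis window? |
|---|---|---|---|
| On treatment | scheduled | scheduled | yes |
| End of treatment | scheduled | scheduled | yes |
| Follow-up | if needed | none | yes |

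The third row is the mismatch. Nothing elsewhere in the SAP limits these worst-case tables to the first two rows.

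**2. Direction.** Adding exams to a maximum cannot lower it, so the third row can only raise Arm 1. For a corneal or lens item recorded as absent or present, an eye already positive cannot shift again. Extra exams then matter only for other items, the other eye, or a deeper visual-acuity category.

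**3. Illustrative size.** None of these inputs is in the SAP:

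- the same constant monthly hazard h of a new ocular abnormality in both arms, so no drug effect;
- exponential time on treatment with median 4 months in both arms, so λ = ln 2 / 4 = 0.173 per month;
- a share s of Arm 1, unrelated to whether an abnormality has already occurred, with f further months of exams.

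Arm 2: P2 = h / (h + λ). Arm 1: P1 = P2 + (1 − P2) × s × (1 − exp(−h f)).

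For h = 0.05, s = 0.3, f = 3: P2 = 0.05 / 0.223 = 22.4%; P1 = 0.224 + 0.776 × 0.3 × 0.139 = 25.6%.

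| h per month | Arm 2 | Arm 1, s = 30%, f = 3 / 6 | Arm 1, s = 100%, f = 3 / 6 |
|---|---|---|---|
| 0.02 | 10.3% | 11.9% / 13.4% | 15.6% / 20.5% |
| 0.05 | 22.4% | 25.6% / 28.4% | 33.2% / 42.5% |
| 0.10 | 36.6% | 41.5% / 45.2% | 53.0% / 65.2% |

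With 30% followed, the gap runs from 1.6 to 8.6 points; at h = 0.05 it is 3.2 to 6.0 points. If the follow-up exams go only to eyes already positive on an item, the gap for that item is zero.

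**4. What a cut at end of treatment does not remove.** Treatment continues until progression unless stopped earlier (Section 1.2), and Section 5.2 expects median PFS of 7 against 4 months. Suppose that time on treatment follows PFS, and again take h = 0.05 in both arms. With fixed times, 1 − exp(−0.05 × 4) = 18.1% against 1 − exp(−0.05 × 7) = 29.5%. With exponential times, 22.4% against 0.05 / (0.05 + ln 2 / 7) = 33.6%. A gap of about 11 points remains after the cut, from longer treatment alone.

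**The case against.** The case on the other side is substantial, and most of it limits the size of the point.

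- **Follow-up exams are conditional.** This stands. Only some of Arm 1 will have them. The SAP does not define need; if it means an unresolved finding, the extra exams go mainly to people who already count as shifted.
- **The tables are descriptive.** This stands. There is no test, and any distortion counts against the experimental arm. Keeping late toxicity in the main table is a legitimate safety choice, which is why that version should remain.
- **Other displays use the same rule in both arms.** This stands. Adverse event displays use the treatment-emergent window of Section 6.2.3; Section 4.5.2.1 gives cumulative incidence by cycles received for each event of special interest; Section 4.5.3.2 gives KVA grade by visit. A reader might infer that the drug's ocular effect cannot be told apart from extra looks. Given these displays, the SAP does not support so broad a statement.
- **Stopping at end of treatment does not equalise observation.** This stands, as step 4 shows. Under those assumptions the residual gap exceeds that from conditional follow-up in 30% of Arm 1.
- **Display details are left to the Output and Programming Specification.** This does not answer the point, because the SAP itself fixes the window.
- **Section 4.5.3.1 does not itself say that results are shown by arm.** True, but it covers exams in both arms and serves an objective worded as one treatment against the other.

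**Conclusion.** The point holds as a modest one. Section 4.5.3.1 takes worst-case ocular results over a window whose last part is examined in Arm 1 only, and asks for post-exposure outcome and resolution that Arm 2 can hardly supply. The direction is towards more, or more severe, worst-case findings in Arm 1.

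The size cannot be computed from the SAP. The figures in step 3 show only how it depends on unknown rates, the share followed and the length of follow-up; zero for a given item is possible. A reader might infer a definite inflation by treating every Arm 1 participant as having three extra independent exams: at 3% per exam, 1 − 0.97^6 = 16.7% against 1 − 0.97^9 = 24.0%, a gap of about 7 points. The SAP supports neither the exam counts nor the rate, and its condition that follow-up exams occur only if needed contradicts giving them to everyone.

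No hypothesis test, error rate or efficacy result is affected. It is a cheap improvement to the safety display, not a flaw that endangers the trial's conclusions.

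**What to change.** In Section 4.5.3.1:

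- add a version of the between-arm worst-change and worst-case shift tables (visual acuity, cornea, lens) limited to baseline through the end-of-treatment exam in both arms;
- keep the version to last follow-up, with findings first seen, or worsened, at Arm 1 follow-up exams identified;
- present outcome and time to resolution after exposure for Arm 1 only;
- state that the common-window version removes the difference made by arm-specific follow-up but not differences in time on treatment, and that by-visit or by-cycle displays should be read alongside. Cycles are 21 days in Arm 1 and 28 in Arm 2 (Section 1.2), so by-cycle figures are not matched on calendar time.

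The cost is a few sentences of SAP text and one more version of existing tables. No exam is added and no conduct changes. The common-window version omits late Arm 1 findings, but these stay in the last-follow-up version.
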